#### Outcome variables and endpoints:

##### Primary outcome:

To confirm that the use of Hiprex will decrease the recurrence of symptomatic UTIs, our primary outcome will be the number of UTI events (namely UTI symptoms with positive urine cultures, or UTI-like episodes requiring antibiotic treatment) during the 1 year of the study period.

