### 3. Concise Summary of Project:

#### Study Design:

[figure not shown]
There will be two parts to this project. Part 1 will be a prospective assessment of the urinary effects of Hiprex in women with RUTIs, such as acidity and concentration of formaldehyde, to determine the best oral concentration to inhibit bacterial growth in urine for each enrolled patient. Part 2 will be a long-term assessment of Hiprex on RUTI evolution in women with a longstanding history of RUTIs, with Hiprex taken at a proper dosing (as established in Part 1) and with regular urine checks at subsequent visits up to one year of follow-up.

Part 1: Women between age 50 and 85 presenting to the outpatient UTSW Urology clinic who are currently taking Hiprex (or any methenamine-containing product) or are willing to be started on Hiprex and do not meet exclusion criteria (see below) will be invited to participate in the study. During their first study visit (V1), they will be consented for this long-term prospective study. The documentation of RUTI based on the current definition of 3 documented and treated UTIs in the past year or 2 in the past 6 months will be recorded. A 3 day diary with recordings of urine pH before each meal and before bed will be obtained to document that the patient has consistent low urine pH (<6), a critical condition for methenamine conversion to formaldehyde. Then the patient will be asked to take a tablet of Hiprex 1gm and to provide one subsequent urine samples at 1 hour after the intake of Hiprex. These midstream urine samples will be processed and transferred to our Lab on campus (K2 building) before being sent to our partnering lab at UTD run by [name] for testing, including urine pH testing, and the measurements of methenamine and aldehyde produced in these urine samples.

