#### Recruitment:

All patients will be recruited from the urology practice of the PI (WCB3 4th floor).

As part of a pilot study, we plan on enrolling 100 patients over 18 months to gather sufficient data to power a more extensive randomized control trial later on, using either a placebo or a competitive low-dose antibiotic, such as Macrobid or Septra, based on the efficacy of Hiprex given at the proper dosing and in the right urinary pH milieu in this small cohort of RUTI women. The PI is raising the enrollment goal due to COVID being tentatively over and the team is able to recruit more subjects due to this.

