## **6. Criteria for Inclusion of Subjects:**

- a. Female
- b. Age 50 – 85
- c. Have RUTIs (at least 2 UTIs within the past 6 months or 3 within the past year)

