## 14. Biostatistics:

Since this is a pilot study, our goal is to enroll 100 patients with RUTIs willing to be closely monitored for 1 year on Hiprex once the appropriate dosing has been confirmed. The acquired data will inform power calculations for a future randomized control trial.

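### The primary aim is to confirm that Hiprex lowers UTI recurrence, but a single-arm study that enrols women on a high recent UTI count can only estimate the on-treatment rate

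*Combined protocol and SAP*

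**What the plan says.** Section 3, Primary outcome, gives the aim and measure: "To confirm that the use of Hiprex will decrease the recurrence of symptomatic UTIs, our primary outcome will be the number of UTI events". Events are counted "during the 1 year of the study period". They include symptomatic, culture-positive UTIs, "or UTI-like episodes requiring antibiotic treatment". No baseline period or comparator is named for this outcome.

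Section 6 sets the entry rule: "Have RUTIs (at least 2 UTIs within the past 6 months or 3 within the past year". The Study Design part of Section 3 describes the qualifying history as "3 documented and treated UTIs in the past year or 2 in the past 6 months". Women already on a methenamine product and women willing to start are both eligible.

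No concurrent control is described. Under Recruitment, a comparator belongs to a later randomised trial, "using either a placebo or a competitive low-dose antibiotic, such as Macrobid or Septra", and that trial is to be planned "based on the efficacy of Hiprex given at the proper dosing and in the right urinary pH milieu in this small cohort". Section 14 gives a target of 100 women and says: "The acquired data will inform power calculations for a future randomized control trial". It contains no test, baseline period or allowance for regression to the mean. The only explicit comparison with the time before Hiprex is a secondary outcome, on hospital admissions and intravenous antibiotics.

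**The concern.** To confirm a decrease, one needs to know what the count would have been without the drug. With one arm, the only stand-in is each woman's own past. The entry rule selects on that past, so it contains some women with a steadily high rate and others who had a bad year by chance. The second group improves without treatment.

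Two consequences follow. A fall in the study year could be reported as confirmation of efficacy when part or all of it comes from selection. And if that fall were taken as the expected effect in the later randomised trial, the trial would be planned on too large a benefit.

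**Working it through.** **Plan's own figure.** There is none to reproduce. The 100 women come with no alpha, power, effect size, baseline rate, dispersion or dropout.

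**Inputs from the documents.** Entry requires at least 2 UTIs in the last 6 months or at least 3 in the last 12. Follow-up is 12 months, with n = 100.

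**Assumptions (not in the documents).** Each woman has a constant annual rate drawn from a gamma distribution with mean m (UTIs a year in the pool of women from which the eligible are drawn) and shape k (a smaller k means women differ more). Counts are Poisson given the rate. The drug effect is zero. The test is a paired t-test, two-sided 5%, counting only significant falls.

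**Formula.** In this model, given a prior-year count y, the expected count in the next year is (k + y)/(k/m + 1). Averaged over eligible women, y is replaced by their mean prior-year count. The simulation supplies that mean and the rejection rate, and the formula lets the fall be checked by hand:

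- m = 1, k = 1: (1 + 3.60)/(1 + 1) = 2.30; fall 1 − 2.30/3.60 = 36%
- m = 1, k = 2: (2 + 3.25)/(2 + 1) = 1.75; fall 46%
- m = 2, k = 1: (1 + 4.67)/(0.5 + 1) = 3.78; fall 19%
- m = 2, k = 2: (2 + 4.08)/(1 + 1) = 3.04; fall 26%

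**Results with zero drug effect** (3 million simulated women per row; 20,000 samples of 100 eligible women):

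| m | k | Year before | Year after | Fall | Test positive |
|---|---|---|---|---|---|
| 1 | 1 | 3.60 | 2.30 | 36% | 100% |
| 1 | 2 | 3.25 | 1.75 | 46% | 100% |
| 2 | 1 | 4.67 | 3.78 | 19% | 91% |
| 2 | 2 | 4.08 | 3.04 | 26% | 99% |
| 3 | 0.5 | 7.02 | 6.44 | 8% | 37% |
| 3 | 1 | 5.69 | 5.02 | 12% | 58% |
| 3 | 2 | 4.92 | 4.15 | 16% | 78% |
| 4 | 0.5 | 8.33 | 7.85 | 6% | 24% |
| 4 | 1 | 6.71 | 6.17 | 8% | 35% |
| 4 | 2 | 5.76 | 5.18 | 10% | 46% |

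Without selection, the chance of a significant fall would be about 2.5%. Separate runs of the same model differ by a few percentage points in the last column.

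**An earlier baseline year.** In this model, months −24 to −13 have the same mean as the null follow-up year (2.30 and 2.30 at m = 1, k = 1), because entry depends only on the last 12 months. If women were in effect also selected on that earlier year, the protection goes. Requiring at least 3 UTIs in it as well gives null falls from that baseline of 27%, 39%, 14% and 20% in the first four settings.

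**Not simulated.** Women start Hiprex culture-negative, and women who cannot reach a low urine pH leave the longitudinal part (Section 4). Both could add to an apparent fall.

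**The case against.** The strongest reply is that this is a pilot. It may properly run without a control, and it defers the comparison to a randomised trial. That stands and lowers the severity, but it does not support a confirmatory aim.

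It can also be said that Section 14 plans no before-after test. That is correct: the test above is a device for showing the size of the artefact, not the plan's analysis. Still, a decrease has no other reference point in this design.

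A reader might infer four stronger things that the documents do not support:

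- **A before-after test would nearly always be positive.** This holds at clinic means of 1–2 a year, which is an assumption. The Study Design section describes a longstanding history of recurrence. If that means stable high rates, the artefact is small and the test is positive in as few as about a quarter of null studies.
- **The later trial will be underpowered by a known amount.** Section 14 says only that the data will inform its power calculation. It does not say that the before-after reduction will be the effect size, and an antibiotic comparator remains open.
- **The broader on-study event definition inflates the benefit.** Counting antibiotic-treated UTI-like episodes, some of which might be the bladder stinging listed as a side effect in Section 2, raises the on-study count and makes Hiprex look worse. The entry history is also not defined as culture-confirmed. The periods may not be comparable, but the mismatch does not explain a fall.
- **An earlier look-back year is a clean baseline.** It may be selected too, and for current methenamine users it may be time on the drug.

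**Conclusion.** The point holds. The stated aim is to confirm a decrease, and a single-arm study with this entry rule cannot do so. With zero drug effect, the count fell in every setting tested: by about 19–46% at clinic means of 1–2 UTIs a year with shape 1–2, and by about 6–16% at means of 3–4 with shape 0.5–2. A paired test in 100 women would be positive in about 91–100% and 24–78% of null studies respectively.

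These sizes rest on assumed rates, an assumed spread between women, constant underlying rates and a test that the plan does not name. The direction follows from the entry rule. For women already on methenamine, selection on recent counts applies as well, but their prior year is not a clean period before treatment.

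This should be fixed. The design is acceptable for a pilot; the aim, and the use of observed efficacy to plan the next trial, are what need to change.

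**What to change.** 1. Reword the primary aim to: To estimate the on-treatment rate of symptomatic UTI over 1 year, with 95% CI. State that a before-after change is not evidence of efficacy.
2. Carry only the on-treatment rate, its overdispersion and retention into planning of the randomised trial, not the before-after reduction. Amend the Recruitment text and Section 14 to say so.
3. Report new starters and women already on methenamine separately.
4. Report culture-confirmed symptomatic UTI and antibiotic-treated culture-negative episodes separately. If any before-after contrast is shown, use one definition in both periods.
5. Months −24 to −13 may be shown as a supporting display in new starters only, with the caveat that this year may also be selected and incompletely recorded. Section 4 lists prior culture data from EPIC but gives no look-back length and no symptom history.

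The cost is protocol wording, two extra breakdowns and, if the display is wanted, a longer look-back in the record extraction. The downside is a more modest claim.

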##### Secondary outcomes:

- Severity of UTI symptoms based on validated questionnaire, with the expectation of a decrease in UTI symptom severity while on Hiprex.

- Duration of intervals between UTI episodes considering that Hiprex may lessen the frequency of oral antibiotics usage to treat symptomatic UTI episodes.
- Reduction in number of hospital admission and IV antibiotics (PICC line) for urosepsis and/or pyelonephritis compared to the pre-Hiprex situation.
- Frequency and severity of adverse effects related to Hiprex, requiring treatment interruption, dose adjustment, or discontinuation.
- Evaluation of possible gradual increase in bacterial resistance to formaldehyde by testing its concentration in the urine at each visit, urine acidity, and ability to kill established bacterial strains (UTI89, CFT073)

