#### Part 2:

Patients already on a methenamine drug will be queried on the history of their exposure (duration of intake, effect on RUTI, current urine pHs, etc). Patients will provide a urine sample. If the urine culture is negative, the patient will begin their prescription of Hiprex by manufacturer recommendations (if not already doing so). If the urine culture returns positive, they will be treated with a course of culture-based antibiotics and will begin Hiprex once their urine results confirm a negative culture.

Based on our preliminary data on seven women followed for one year, the levels in urine (ratioed to urinary creatinine to account for urine dilution) remain fairly stable over time.

Therefore, we don't need to follow women on Hiprex as closely as we intended to at the start of this project. Now we suggest that patients return to clinic at 3 months, 6 months, and 12 months after the onset of their Hiprex treatment to provide urine samples. During these follow-up visits, patients will also fill out a standardized, validated questionnaire regarding UTI symptoms. Data concerning common Hiprex side-effects and compliance with self-administration of Hiprex will also be collected. Hiprex will be stopped when clinically indicated based on the onset of such side-effects. Urine acidity and concentration of methenamine and formaldehyde will be analyzed in these urine samples. Hiprex dosage will be increased if concentration of formaldehyde is not above the threshold for bacteriostatic effects.

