#### **4. Study Procedures:**

##### Initial visit:

Patients will be consented for the study. Patients will also be advised to return to clinic sooner than scheduled follow-up visits if they start to develop symptoms of a UTI (pain with urination, cloudy or bloody urine, etc.) or experience any side-effects that may be attributed to Hiprex. Patients who have previously been on a methenamine-containing substance will be asked about their medication history, including the length of time on the medication, the dosage and any changes to dosage, and side-effects experienced while taking the medication. Patients will be prescribed Hiprex 1 g PO BID for 3 months with 4 refills (total of 1 year). Urine samples will be obtained from patients prior to their first dose intake. Those will be mid-stream urine sample, with a collection volume around 30 ml.

Those with negative cultures (after 48-72 hours) will begin their first dose of Hiprex. Those with positive cultures will be treated with a course of culture-based antibiotics and will start their first dose of Hiprex when they can produce negative urine cultures. Using a formaldehyde assay, the concentration of formaldehyde in the urine samples with negative cultures of each patient will be measured. A pH meter will be used to determine the acidity of the urine samples.

In the lab of [name], the following studies will be performed on de-identified urine samples:

**Sample preparation:** The urine samples will be frozen at  $-80^{\circ}\text{C}$ . Upon thawing for assay, the urine will be adjusted to pH 8.0 by adding 50 mM HEPES buffer and checked with pH paper in order to prevent methenamine breakdown, which occurs rapidly at  $\text{pH} < 6$ . The sample will be centrifuged to remove particulates and the soluble portion filter sterilized.

**Formaldehyde assay:** A variety of formaldehyde assays are available (summarized in X1). We will use a glutathione-dependent formaldehyde dehydrogenase (FDH)-based assay (X2). The urine sample will be diluted 10- to 1000-fold and placed in a microtiter dish well. The reaction will also contain 50 mM HEPES buffer (pH 8), 0.5 mM reduced glutathione, 0.5 mM NAD, and FDH (the FrmA protein) purified from *Escherichia coli*. The increase in NADH is proportional to the amount of formaldehyde. The mM extinction coefficient for NADH is 6.27. To ensure the linearity of the reaction, a known amount of formaldehyde will be added to this reaction in a separate reaction.

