#### Follow-up:

Patients will be asked to return to clinic for 3 follow-up visits at: 3 months (V1), 6 months (V2), and 12 months (V3) after starting Hiprex. This research visit timing corresponds to standard-of-care clinic visits include those at 3 months, 6 months, and 12 months.

At each of these visits, patients will be asked to withhold their first dose of Hiprex until they arrive to clinic. Urine samples will be collected at baseline, then 1 hours after the dose intake. These samples will be tested according to the same protocol in the lab of [name]. In addition, patients will be administered a UTI Symptom Assessment (UTISA) questionnaire and queried about any UTI symptoms and Hiprex-associated symptoms since their last visit. If the concentration of methenamine/formaldehyde in the urine sample is found to be inadequate for bacteriostatic or bactericidal activity, the dosage might be increased to 1.5 PO BID, and/or diet-adjustment might be considered to decrease urine pH if found to be not sufficiently acidic. For patients unable to reach appropriate low pH urinary levels after the above modifications, they will be removed from the study and will not continue with the longitudinal portion.

Data:

The dataset will be extracted from EPIC and will include demographic data (age, gender, race, height, weight) as well as culture data from prior urinary tract infections, comorbid conditions (i.e. diabetes, renal insufficiency, etc.), hormonal status, methenamine usage history, and urological history (including possible surgical interventions). See Excel document.

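### The symptom-severity outcome expects a decrease on Hiprex, but no UTISA is scheduled before the first dose or at a symptomatic visit, so a decrease from the pre-Hiprex level cannot be assessed

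*Combined protocol and SAP*

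**What the plan says.** Section 3 (Secondary outcomes) includes "Severity of UTI symptoms based on validated questionnaire, with the expectation of a decrease in UTI symptom severity while on Hiprex". The outcome states a direction but names no reference value.

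Two places give the timing of the questionnaire:

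- Section 3 (Part 2): "During these follow-up visits, patients will also fill out a standardized, validated questionnaire regarding UTI symptoms".
- Section 4 (Follow-up): "patients will be administered a UTI Symptom Assessment (UTISA) questionnaire and queried about any UTI symptoms and Hiprex-associated symptoms since their last visit". The visits concerned are at "3 months (V1), 6 months (V2), and 12 months (V3) after starting Hiprex".

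The first visit is described in Section 3 (Study Design, Part 1) and Section 4 (Initial visit). Between them these list consent, documentation of recurrent UTI, methenamine history, a urine pH diary, urine sampling, culture, and the formaldehyde and pH measurements. Neither lists a symptom questionnaire.

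The Initial visit text also says that women are "advised to return to clinic sooner than scheduled follow-up visits if they start to develop symptoms of a UTI". It attaches no UTISA to that visit.

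Section 14 (Biostatistics) gives a target of 100 patients and no analysis or comparison for this outcome.

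**The concern.** A decrease needs something to decrease from. In a single-arm study the natural reference is the patient's own severity before the drug, and the schedule does not collect it. A pre-treatment score that was not taken cannot be recovered once Hiprex has started.

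There is a second gap, in timing. The title of reference 31 describes the instrument as a measure of the severity and bother of symptoms in uncomplicated UTI. The plan gives it at routine visits, not when an infection brings the woman to the clinic, so most infections would have no score.

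The stated use of the pilot is to help size a later randomised trial. For this outcome it would supply neither a change from pre-treatment to on-treatment nor the variability of that change, and it would supply few scores from actual episodes.

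**Working it through.** The plan gives no effect size, standard deviation or power for this outcome, so there is no figure of its own to reproduce. The check is a count of the schedule, followed by an illustration of how often a routine visit would meet an infection.

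**Step 1. Scheduled UTISA administrations per patient**

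- Before the first dose: 0 (Section 3, Study Design and Part 2; Section 4, Initial visit).
- On treatment: 3, at months 3, 6 and 12 (Section 4, Follow-up).
- Triggered by a UTI episode: 0 (Section 4, Initial visit, asks for an early return but no questionnaire).

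Across the planned 100 women that is 100 × 0 = 0 pre-treatment scores. The within-patient changes that can be formed are month 3 to 6, 3 to 12 and 6 to 12, all on treatment.

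**Step 2. Could other wording supply a baseline?**

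- The label V1 is used twice. In Study Design it is the consent visit: "During their first study visit (V1), they will be consented for this long-term prospective study". In Follow-up it is the 3-month visit. The UTISA belongs to the Follow-up set, which is defined as after the start of Hiprex, so the shared label creates no pre-treatment score.
- The baseline mentioned under Follow-up is the pre-dose urine sample at each of those visits.
- At the first visit, "Urine samples will be obtained from patients prior to their first dose intake". That is a specimen, not a symptom score.
- There is no control group to stand in for a missing baseline.

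**Step 3. Share of episodes that meet a scheduled visit (illustrative)**

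The documents give neither the length of an episode nor the UTI rate on treatment. Assume that an episode lasts D days, that visit dates are unrelated to symptoms, and that the UTISA reflects symptoms at the time of completion. With 3 visits in 365 days, and visits too far apart for one episode to meet two of them, the share of episodes scored is 3 × D / 365, whatever the UTI rate:

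- D = 3: 9/365 = 2.5%
- D = 7: 21/365 = 5.8%
- D = 14: 42/365 = 11.5%

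With an assumed 1 to 3 episodes per woman per year, 100 women followed for the full year have 100 to 300 episodes. The expected number scored is about 2 to 7 for D = 3, 6 to 17 for D = 7, and 12 to 35 for D = 14.

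**Step 4. Share of women with an episode at any of the three visits**

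With r episodes per year, p = r × D / 365 per visit. Treating the visits as independent, the chance for at least one visit is 1 − (1 − p)³:

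- D = 7: p = 1.9% to 5.8% for r = 1 to 3, giving 5.6% to 16.3%.
- D = 14: p = 3.8% to 11.5%, giving 11% to 31%.

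The result depends strongly on the assumed duration, so these are ranges and not estimates.

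**The case against.** The strongest reply has four parts.

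1. *A decrease can be computed.* Three on-treatment scores allow a change from month 3 to month 12, and the outcome speaks of severity while on the drug. Only another secondary outcome, on admissions and IV antibiotics, names the pre-Hiprex period as its comparator. This stands in part. A reader might infer that no decrease of any kind can be measured, and the documents do not support that. But a change starting at month 3 misses the first three months and does not show what starting Hiprex did. Reading the outcome as a fall from the pre-Hiprex level is an inference, though the natural one.

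2. *Symptoms between visits are not ignored.* The Follow-up text adds a query about symptoms since the last visit, and a woman may happen to be symptomatic at a routine visit. Both are true. A reader might infer that the UTISA is never completed during a UTI; the text supports only that none is scheduled for one. The query is listed separately from the UTISA and is not described as a scored severity measure for an episode, so it does not fill the gap. The documents give no recall period for the UTISA, which is why the percentages are conditional.

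3. *The harm is speculative.* A reader might infer that low follow-up scores would be presented as a drug benefit. The plan specifies no analysis of this outcome, so nothing in the text supports that prediction.

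4. *A baseline score alone does not solve it.* Recruitment includes women already taking methenamine, who have no untreated state to score. New starters begin only after a negative culture, so a score taken then may describe a time between episodes. Comparing only symptom-free assessments would not measure UTI severity, and on-treatment episode scores have no counterpart unless a symptomatic pre-treatment visit was scored. This stands and shapes the fix.

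**Conclusion.** The point holds for a decrease from the pre-Hiprex level. The plan schedules no UTISA before treatment, three on treatment and none tied to a symptomatic visit, and it has no control group. It therefore cannot show the fall in severity that the outcome anticipates. That conclusion rests on the text alone, with one limit: the data-collection spreadsheet mentioned in Section 4 is not part of the documents and could not be checked.

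The size of the second gap rests on assumptions. With episodes of 3 to 14 days, visits unrelated to symptoms and a UTISA that reflects current symptoms, about 2.5% to 11.5% of episodes would be scored, leaving roughly nine in ten or more without a score.

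This is one secondary outcome in an uncontrolled pilot. It does not touch the primary outcome, but it should be corrected because the correction is cheap and the missing scores cannot be obtained later.

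**What to change.** **Collection.** Administer the UTISA:

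- at the initial visit before any Hiprex is taken, including when the woman is symptomatic or culture-positive and has not yet had antibiotics, and record symptom status, culture result and current methenamine use with it;
- at each unscheduled clinic visit for UTI symptoms;
- at months 3, 6 and 12, as now planned, recording symptom and culture status there too.

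**Endpoint.** Define change from the pre-treatment UTISA in new starters only, comparing assessments of like symptom and culture status. Report women already on methenamine separately, since their enrolment score is not an untreated baseline. Report episode-level UTISA on treatment descriptively, as input to the later randomised trial, and claim a decrease in episode severity only where a pre-Hiprex symptomatic score exists. Give the consent visit and the 3-month visit different labels.

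**Cost.** A few minutes of patient time per visit and a short addition to the schedule. The change analysis will rest on fewer than 100 women if current users enrol; the documents do not say how many are expected. Episodes treated outside the study clinic will still have no score. Treatment is unaffected.

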There are **several studies reporting on the efficacy of Hiprex**; however, most only include patients with specific comorbid conditions. After excluding men, Table 1 includes a review of these studies. A case series found that the administration of Hiprex resulted in a decrease in catheter changes among patients with indwelling catheters. Another long-term study reported that, after starting Hiprex, a decrease in the rate of reinfection of UTIs in geriatric patients hospitalized was noted at two years, especially in those who were supervised while taking their medications; however, the rate of UTIs prior to starting Hiprex was not given. A review of Hiprex, containing 2032 patients across 13 studies, indicated that short-term treatment (1 week or less) of Hiprex in women without renal tract abnormalities led to a significant decline in UTIs. However, the authors admitted that given the heterogeneity in the populations studied and the outcomes measured, there was no clear consensus amongst these studies.

Although the literature offers no recommendation for the length of time to prescribe Hiprex, the current knowledge on Hiprex suggests a possible role of longer courses to fully evaluate its

efficacy in the management of RUTIs. Fortunately, many women evaluated for RUTIs will not have any of the examined comorbid conditions as listed in Table 1, and many will present without an overt risk factor for UTIs; thus, it is important to include these women in future studies.

**Hiprex can cause various mild side-effects**, such as rashes, diarrhea, sore throat, abdominal pain, and bladder “stinging”. Although the side-effects are typically self-limited and non-severe, hemorrhagic cystitis was found in the case of an accidental ingestion of 8 g of methenamine mandelate by a 2½-year-old. Despite the side-effect being due to a different formulation of methenamine from Hiprex as well as the dose being much higher than the recommended maximum of 500 mg, this rare case still underlines the importance of ensuring that Hiprex is effective enough so that its benefit outweighs its potential risks.

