## **11. Subject Safety and Data Monitoring:**

Patients will be offered Hiprex, which, based on available literature since the 1960s, has not been known to lead to any serious or long-lasting side effects. However, patients will be given all relevant warnings and queried about new symptoms at each follow-up visit. Hiprex will be stopped when clinically indicated. Once the patient data has been analyzed, the data will be archived in a password-protected repository.

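### The only safety outcome counts adverse effects that are related to Hiprex and also force a treatment change, so the milder side-effects the protocol expects and collects drop out of the reported result.

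*Combined protocol and SAP*

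**What the plan says.** All references are to the combined protocol and SAP.

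- **Section 3, Secondary outcomes.** The one safety outcome is "Frequency and severity of adverse effects related to Hiprex, requiring treatment interruption, dose adjustment, or discontinuation". The section also counts hospital admissions and IV antibiotics, but only for urosepsis or pyelonephritis.
- **Section 2, Background.** The listed side-effects are "rashes, diarrhea, sore throat, abdominal pain, and bladder" stinging. On their course it says: "Although the side-effects are typically self-limited and non-severe".
- **Section 3, Part 2.** "Data concerning common Hiprex side-effects and compliance with self-administration of Hiprex will also be collected". No treatment-change condition is attached.
- **Section 4, Follow-up.** Women are "queried about any UTI symptoms and Hiprex-associated symptoms since their last visit". If urinary concentrations are inadequate, "the dosage might be increased to 1.5 PO BID". Women whose urine pH stays too high after modification are removed from the study.
- **Section 11.** Women are "queried about new symptoms at each follow-up visit".
- **Section 14, Biostatistics.** It gives the target of 100 and the aim of informing power calculations, but no safety analysis.

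No section says who judges relatedness, by what rule, or on what severity scale.

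**The concern.** An outcome that sets two conditions before an event is counted can report little harm while many women have side-effects. Here the second condition, a treatment change, works directly against the kind of effect the Background leads one to expect: a mild, self-limited complaint is the least likely to make anyone interrupt, adjust or stop a drug. The study would ask about such complaints and record them, yet the defined outcome would not report them.

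The first condition, relatedness, has a different weakness. Every woman takes Hiprex openly and any comparator is left to a later trial, so a judgement that a symptom is or is not due to the drug cannot be checked against anything.

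What is at stake is the tolerability description from a one-year pilot meant to prepare a randomised trial. The primary outcome is not affected.

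**Working it through.** The plan gives no safety figure to reproduce: it states no adverse-event rate, and the target of 100 comes with no alpha, power or effect size. The check is mainly a comparison of the text.

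**Step 1: what is collected against what is reported.**

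| Place | Scope | Relatedness condition | Treatment-change condition |
|---|---|---|---|
| Section 11 | New symptoms | No | No |
| Section 4, Follow-up | UTI symptoms and Hiprex-associated symptoms | Yes, for the non-UTI part | No |
| Section 3, Part 2 | Common Hiprex side-effects | Limited to known effects | No |
| Section 3, Secondary outcomes | Reported safety outcome | Yes | Yes |

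The treatment-change condition appears only in the reported outcome. The three descriptions of the enquiry also differ in breadth; only Section 11 is broad.

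**Step 2: direction of each condition.** The counted set is the intersection of related events and events with a treatment change, so it cannot exceed the set of all events. Among related effects, the treatment-change condition can only remove. The relatedness judgement can err both ways: drug effects may be called unrelated, and unrelated symptoms in women aged 50 to 85 followed for a year may be called related.

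**Step 3: illustration under assumed rates.** None of these rates is in the documents. Let *a* be the share of women with any adverse event (assumed 20–60%), *r* the share of those judged related (30–90%), and *c* the share of related ones leading to a treatment change (10–50%).

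Share of women with an event who are counted = *r* × *c*:

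- low: 0.30 × 0.10 = 3%
- middle: 0.60 × 0.30 = 18%
- high: 0.90 × 0.50 = 45%

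Middle case with 100 evaluable women and *a* = 40%:

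- any event: 100 × 0.40 = 40 women (exact 95% interval for 40/100: 30.3–50.3%)
- judged related: 40 × 0.60 = 24 women
- counted by the outcome: 24 × 0.30 = 7.2, about 7 women (exact 95% interval for 7/100: 2.9–13.9%)

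The treatment-change condition alone removes 1 − *c* of related effects: 70% in the middle case, and 50–90% over the assumed range. These figures show how the definition behaves; they do not estimate this study's under-count.

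**The case against.** The strongest reply is that the data are not lost. Common side-effects are collected without the treatment-change condition, and nothing forbids a fuller table. That is right: the gap is in the defined outcome, not in all of the data collection. But a plan should say what will be reported, and this one commits only to the filtered count. It can also be said that the comma before the treatment-change clause leaves some ambiguity. If all related effects were meant, the text should say so.

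A second reply is that counting every symptom in an uncontrolled study overstates harm caused by the drug. This stands. The full count is not a true rate of drug harm, which is why relatedness should be a recorded attribute rather than dropped.

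A reader might infer several stronger points that the documents do not support:

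- **That attribution moves episodes between efficacy and safety, because bladder stinging resembles UTI burning.** The primary outcome needs symptoms with a positive culture, or a UTI-like episode requiring antibiotics. Attribution to Hiprex is in neither limb, and nothing makes the two outcomes mutually exclusive.
- **That all new symptoms are already asked about, so the change is free.** Only Section 11 is worded broadly, and no severity scale or onset date is described.
- **That an excess after a dose increase will be hidden.** The plan promises no by-dose table, but it does not prevent one, and Section 4 makes the increase conditional.
- **That side-effect rates will be carried into the later trial.** The protocol mentions efficacy and power calculations in that context, not side-effect rates.

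**Conclusion.** The point holds in a limited form. As worded, the only safety outcome omits related effects that cause no treatment change, although the protocol expects mostly mild effects and collects common ones. That most expected effects would be dropped is an inference: it assumes that self-limited, non-severe effects seldom lead to interruption, adjustment or stopping.

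The direction is certain for the treatment-change condition and open for the relatedness judgement. It would therefore go too far to say that drug-caused harm as a whole must be understated. The size is unknown: the 3–45% range above rests wholly on assumed rates. The change is a cheap improvement in reporting and does not bear on the validity of the primary outcome.

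**What to change.** 1. Define the safety outcome as all new or worsened symptoms reported at each visit, in every woman who took at least one study dose, including those later removed from the study.
2. Tabulate by severity and by dose at onset. Show those judged related and those leading to a treatment change as subsets, so the present definition is kept. State who judges relatedness, by what rule, and which severity scale is used.
3. Reconcile the symptom enquiry in Section 3 (Part 2), Section 4 (Follow-up) and Section 11 to the broader Section 11 wording.
4. If wished, show urinary burning with its culture result in the safety table, for description only. It must not alter the primary-outcome definition, which deliberately includes antibiotic-treated episodes without requiring a positive culture.

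Cost: no added visits or patients and no change in clinical management. A few data fields are needed (severity, onset, action taken). The reported event rate will be higher, and the report should state that without a control arm this rate does not isolate harm caused by the drug.
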